### 8.2. Assessments by Visit

The Schedule of Assessments to be performed for each part of the clinical trial can be found in Table 1.

#### 8.2.1. Screening Period W-2 to Day-1 (hence the screening/recruitment period is up to 2 weeks)

Potential patients for the inclusion in the clinical trial will be informed about the study and asked to attend the Screening Visit within 14 days before receiving the first dose of IMP. The Investigator has to confirm that patients are on standard of care as per the site's SOPs. Written informed consent will be obtained from all patients before any screening procedures are performed. Patients will be fully informed of their responsibilities, of all the procedures expected to be performed in the clinical trial, the possible risks, disadvantages and potential benefits of being dosed with SNF472 and their rights while participating in the clinical trial. They will have the opportunity to ask questions and have time to consider participation. If the patient wishes to participate in the clinical trial, they will be asked to sign and date the ICF.

The Screening Visit will be carried out and a 12-Lead ECG, will be taken, demographic, including body weight (dry weight) and anthropometric data, physical examination, medical history and treatment history (prior medication) data. Safety laboratory assessments (including clinical chemistry, haematology and a serum pregnancy test) will be taken from the routine safety laboratory analysis whenever possible.

The patient will be asked to draw the level of pain experienced on the VAS.

Patients will be considered eligible to participate in the clinical trial if they successfully complete the Screening Visit, meet all the inclusion criteria, and the lesion is considered to fulfil CUA requirements, as per [REDACTED].

Patients can start treatment at any point in time during the initial 2-week period at the PI's discretion or if the PI decides that the patient is not adequately responding to the SOC.

### **8.2.2. Expected Duration of the Clinical trial**

The maximum expected duration for an individual patient of the clinical trial, including Screening and Follow-up, will be approximately 15 weeks.

### **8.2.3. Treatment Period W1-W12**

All eligible patients will receive SNF472 during their haemodialysis sessions. SNF472 will be administered at each dialysis session for the entire duration of the study. The duration of infusion of SNF472 will range from 2.5 h up to maximum time on dialysis, which would be 4 h. SNF472 should NOT be administered directly intravenously. SNF472 should NOT be administered concomitantly with STS, should STS be used. In case both drugs would be administered to the patient, the administration of SNF472 should be stopped 30 minutes before the end of the dialysis session to allow the STS infusion to take place in the last 30 minutes of the session.

In the event of Fe+ administration, the infusion of SNF472 should be stopped BEFORE starting the Fe+ infusion.

For other assessments please check Table 1.

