**Main exclusion criteria:**

1. Body weight above 150 kg
2. BMI  $> 35$  and central(abdominal) ulcers
3. History of bisphosphonate treatment within 12 months before entering into the study
4. Severely ill patients without reasonable expectation of survival for  $> 6$  months according to the treating physician

5. Patients with scheduled parathyroidectomy during the run-in or study period
6. Female patients who are either intending to get pregnant or are undergoing treatment to get pregnant, as well as breast-feeding females
7. Participation in another clinical trial with an experimental drug within 90 days prior the inclusion
8. Any psychological, emotional problems, any disorders or resultant therapy that is likely to invalidate informed consent, or limit the ability of the patient to comply with the Clinical Trial Protocol requirements
9. Patients who, in the opinion of the Investigator, are considered unsuitable for any other reason

**Study  
Procedures:**

Written informed consent will be obtained from all patients before any study-related procedures are performed.

The patient's medical history, demographic, and baseline characteristics, as well as a picture of the wound deemed to be CUA, will be collected to determine the patient's eligibility for inclusion, which will be analysed [REDACTED].

Blood samples taken routinely from patients will be used as source data for the trial.

SNF472 will be administered by infusion at a single, constant dosage for a minimum of 2.5h up to the whole duration of the dialysis session. SNF472 will be administered at three haemodialysis sessions per week for 12 consecutive weeks.

Follow-up assessments including lesion documentation and clinical status will be done at regular intervals (ulcer size, features, Bates-Jensen Wound tool assessment, pain, and Wound QoL) over a period of 12 weeks (see Table 1). Additional assessments will include safety and assessment of pharmacokinetics (PK) and pharmacodynamic (PD) profiles. One sample of blood to measure biomarkers will be taken at the time of PK samples (see Table 1).

During the clinical trial, patients will be monitored closely for any adverse events (AEs). The time points where blood samples will be taken to evaluate safety, PK, PD, and biomarkers are specified in the Table of Assessments (see Table 1).

**Criteria for  
Evaluation:**

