	SCR	TREATMENT PERIOD																														FU						
Week	-2, -1	1			2			3			4			5			6			7			8			9			10			11			12			13
Day		1	3	5	1	3	5	1	3	5	1	3	5	1	3	5	1	3	5	1	3	5	1	3	5	1	3	5	1	3	5	1	3	5	1	3	5	
Treatment History (prior medication) 	X																																					
Medical History	X																																					
Eligibility 	X																																					
CUA Diagnosis	X																																					
Treatment (Intravenous SNF472) 		X	X	X	X	X	X	X	X	X	X	X	X	X	X	X	X	X	X	X	X	X	X	X	X	X	X	X	X	X	X	X	X	X	X	X	X	
Wound QoL Score		X															X																				X	
Pain Score (VAS scale)	X	X			X						X						X						X													X	X	
Lesion Score (BJWAT)		X			X						X						X						X														X	X
Biomarkers		X																																				X
Plasma PK and PD sampling (predose & end of infusion)*		X																																			X	X

 Prior medication includes medications within 6 months of study start

 The inclusion/exclusion criteria will be assessed for each patient at Screening – final entry into the study depends on confirmation by the PI, [name]

 A Treatment Period includes 3 dialysis sessions/week x 12 weeks (36 treatments)

	SCR	TREATMENT PERIOD																														FU									
Week	-2, -1	1			2			3			4			5			6			7			8			9			10			11			12			13			
Day		1	3	5	1	3	5	1	3	5	1	3	5	1	3	5	1	3	5	1	3	5	1	3	5	1	3	5	1	3	5	1	3	5	1	3	5				
Concomitant Medication		X	X	X	X	X	X	X	X	X	X	X	X	X	X	X	X	X	X	X	X	X	X	X	X	X	X	X	X	X	X	X	X	X	X	X	X	X			
Adverse Events		X	X	X	X	X	X	X	X	X	X	X	X	X	X	X	X	X	X	X	X	X	X	X	X	X	X	X	X	X	X	X	X	X	X	X	X	X			
End of Study Visit																																									X

[figure not shown]
[figure not shown]

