### 5.3. Inclusion Criteria

Patients who meet the following criteria will be considered eligible to participate in the clinical trial:

1. Patients with either newly diagnosed CUA OR recurrent CUA that has been dormant with no skin lesion involvement for at least 90 days from study start (new or recurrent diagnosis must be made within 5 weeks of study start)
2. Patients who signed the written informed consent to participate in this clinical trial (prior to any clinical trial-related procedures being performed), after reading the Patient Information Sheet and Informed Consent Form (ICF), and who had the opportunity to discuss the clinical trial with the Investigator or designee
3. Males or females aged  $\geq 18$
4. Patients on maintenance haemodialysis
5. Patients with at least a minimum level of pain on VAS scale or on pain-killers stronger than NSAIDs

6. Females of child-bearing potential should use a highly effective contraceptive measure throughout the study AND have a negative serum pregnancy test at entry. Male patients having sexual relationship in which pregnancy can occur should take adequate contraceptive precautions (wear a condom) (see Section 8.3.1.)

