8.2.3 Efficacy Analysis Set

The definitions given in the protocol about the efficacy analysis sets were considered very restrictive, therefore two new analysis sets for efficacy have been defined:

8.2.3.1 *Intention to Treat Set*

Subjects who have received at least one dose of SNF472 and for whom at least one post-baseline efficacy measurement is obtained.

8.2.3.2 *Per Protocol Set*

The Per Protocol Set includes all subjects who receive at least 75% of SNF472 doses and who did not violate the protocol in a way that might affect the evaluation of the effect of the study drug on the primary endpoint.

Major and minor protocol violations will be identified and documented by the Sponsor.

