9.1.7 Treatment exposure and compliance

The extent of exposure to SNF472 will be characterised according to the number of subjects exposed, the duration of exposure, and the dose to which they were exposed.

The following data will be summarized descriptively for the total treatment period and by week (Shell T-6):

- **Treatment duration (days)** defined as the total number of days between the first and the last infusion dates (inclusive).

-
- **Treatment exposure (infusions)** defined as the number of infusions with the study drug of at least 1 hour that were administered to a subject.
 - **Compliance (%)** defined as the total number of infusions administered to a subject divided by the total number of planned infusions, i.e, 3 administrations x 12 weeks of treatment = 36.
 - **Dose (mg)** presented as a categorical variable indicating the number and percentage of subjects presented on the different planned dose levels (400, 450, 700, and 900 mg).
 - **Total dose (mg) (an estimation of the total dose)**
 - **Dialysis duration (minutes)** defined as the time in minutes registered between the start of the dialysis start and it end.
 - **Infusion duration (minutes)** defined as the time in minutes registered between the start of the infusion and its end.
 - **Number of infusions with any interruptions** counting the number of infusions per subject where the question "Infusion interruptions" is Yes.
 - **Ca in Dialysate Bath** presented as a categorical variable.

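### The every-session and three-sessions-a-week dosing instructions agree only for patients dialysed three times a week, eligibility sets no dialysis frequency, and the SAP's planned count is fixed at 36

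*Protocol*

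**What the plan says.** **Schedule.** The Protocol Synopsis, under Study Procedures, states: "SNF472 will be administered at three haemodialysis sessions per week for 12 consecutive weeks". Table 1, footnote 7, puts a count on it: "A Treatment Period includes 3 dialysis sessions/week x 12 weeks (36 treatments". The treatment rows of the schedules in both documents mark days 1, 3 and 5 of each week. Protocol 8.2.3, the section that tells sites how to treat, states: "SNF472 will be administered at each dialysis session for the entire duration of the study". It gives no weekly number.

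**Eligibility.** Inclusion criterion 4 in Protocol 5.3 reads only "Patients on maintenance haemodialysis". No other criterion in Protocol 5.3 or 5.4, or in SAP 6.3.1 or 6.3.2, mentions how often the patient is dialysed.

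**Dose.** Protocol 6.1 fixes the amount per infusion by weight category (400, 450, 700 or 900 mg) and gives no weekly total.

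**Analysis.** SAP 9.1.7 divides infusions given by the "total number of planned infusions, i.e, 3 administrations x 12 weeks of treatment = 36". SAP 8.2.3.2 admits to the Per Protocol Set "all subjects who receive at least 75% of SNF472 doses", subject to a condition on protocol violations, and names no denominator for the 75%.

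**The concern.** Protocol 10.9 requires the protocol to be followed exactly. For an eligible patient on four or more sessions a week, a site cannot do so: dosing every session departs from the synopsis and footnote 7, and dosing three sessions departs from 8.2.3. For a patient on two sessions a week, 36 infusions in 12 weeks are out of reach.

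Two things depend on this. The first is exposure. Protocol 6.1 uses weight categories to even out exposure between patients, but with a fixed amount per infusion the weekly dose would still depend on which passage the site followed. The second is the compliance figure, and possibly Per Protocol membership, because both rest on a planned count that only one of the two wordings supports. With 15 patients, each one is 1/15 = 6.7% of the sample.

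**Working it through.** **Inputs.** Three sessions a week for 12 weeks (Synopsis; Table 1 footnote 7). Every session (Protocol 8.2.3). Planned infusions 36 (SAP 9.1.7). Threshold 75% (SAP 8.2.3.2). Dose per infusion and weight limits (Protocol 6.1). One-month repeat-dose experience of 10 mg/kg three times a week (Protocol 2.3.2, haemodialysis patients). Sessions per week, f, is an assumption wherever it is not 3.

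**The plan's own figure.** 3 × 12 = 36, which reproduces exactly.

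**The two wordings compared.** Dosing every session gives 12f infusions. Because the dose per infusion is fixed, the weekly dose relative to the three-a-week schedule is f/3. Compliance with full attendance under the SAP formula is 12f/36.

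| f (assumed unless 3) | Infusions, 12f | Weekly dose ratio, f/3 | Compliance, 12f/36 |
|---|---|---|---|
| 2 | 24 | 0.67 | 66.7% |
| 3 | 36 | 1.00 | 100% |
| 4 | 48 | 1.33 | 133% |
| 5 | 60 | 1.67 | 167% |
| 6 | 72 | 2.00 | 200% |
| 7 | 84 | 2.33 | 233% |

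**Weekly dose per kg.** The highest per-kg dose in the table is 700 mg at 81 kg: 700/81 = 8.64 mg/kg per infusion.
- Three sessions: 8.64 × 3 = 25.9 mg/kg/week.
- Four sessions: 8.64 × 4 = 34.6 mg/kg/week.
- Cited one-month experience: 10 × 3 = 30 mg/kg/week.

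At four sessions the 30 mg/kg/week figure is passed only when a single infusion exceeds 30/4 = 7.5 mg/kg. The lowest per-kg dose in the table, 450 mg at 80.9 kg, is 450/80.9 = 5.56 mg/kg. Four sessions of that is 22.2 mg/kg/week, below 30.

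**Per Protocol threshold, if the denominator is 36.** 0.75 × 36 = 27 infusions.
- f = 2, every session attended and dosed: 24 < 27, so the patient is out.
- f = 4, every session intended: the patient can miss 48 − 27 = 21 of 48 sessions and stay in, having received 27/48 = 56% of the sessions.
- f = 4 or more with full attendance: in, whether the denominator is 36 or 12f.
- f = 5 but dosed three times a week: 36/36 = 100%, which is correct.

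**The case against.** The strongest reply is that 8.2.3 is consistent when read in context. Its heading is the treatment period, footnote 7 says that this period comprises 36 sessions, and each session can be read as each of those 36. The day 1, 3 and 5 grid and the SAP denominator fit that reading, and no passage describes a frequency other than three. This stands as evidence of the intended frame. It also means that a reader who infers a contradiction affecting every patient goes too far: for thrice-weekly patients the ratio is 1.00. It does not close the gap, because neither 8.2.3 nor the eligibility criteria say that the patient must be on three sessions.

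It can also be said that final entry depends on central confirmation (Table 1 footnote 6), and that exclusion 9 lets the investigator refuse an unsuitable patient. Both are true, but neither sets a frequency.

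Three stronger readings are tempting and are not supported.

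- *A two-fold dose difference.* This needs exactly six sessions a week, which no passage mentions, and it is not an upper bound, since seven gives 2.33.
- *A breach of a safety limit.* The 30 mg/kg/week figure is cited experience, not a documented limit. The protocol frames safety mainly by peak concentration (2.1.1, 6.2), reports no accumulation (2.3.2), and cites doses up to 20 mg/kg for one week (6.2) and 13-week daily dosing in animals (2.3.2). None of that establishes how a more frequent 12-week schedule would behave in patients, but nor is a hazard shown.
- *Compliance and Per Protocol membership wrong for everyone not on three sessions.* As the cases above show, membership is distorted only for two-session patients, or for frequent-session patients with many missed infusions. The rule does not name 36 as its denominator. The primary endpoint is also analysed in the Intention to Treat Set, which has no 75% rule. The by-week exposure summaries in SAP 9.1.7 would make off-schedule dosing visible.

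**Conclusion.** The concern holds in a limited form. The protocol gives two dosing-frequency instructions that coincide only at three sessions a week, and eligibility does not confine entry to such patients. For anyone else they conflict or cannot be met. The size is f/3 in weekly dose, conditional on an assumed f. At four sessions and the highest per-kg dose in the table, weekly exposure would be above the one-month experience that the protocol cites. The compliance distortion follows directly from the fixed 36. The Per Protocol consequence needs the further assumption that the 75% is taken of 36.

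How many patients would be affected is unknown and may be none. Since the rest of the plan points to three sessions as the frame, this should be fixed but does not rank with errors that must be resolved before the plan can be used. No view is taken on which schedule is right.

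**What to change.** **Protocol.** Reconcile 8.2.3 with the synopsis and Table 1 footnote 7 so that one schedule is stated everywhere. The sponsor's clinical team should state how it applies to a patient not dialysed three times a week, or make dialysis frequency an eligibility condition in 5.3 or 5.4. No schedule is proposed here.

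**SAP.** In 9.1.7, define planned infusions per patient from the reconciled schedule instead of a fixed 36. In 8.2.3.2, refer to that definition so that the 75% has a stated denominator.

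**Cost.** A few sentences across the two documents. If frequency becomes a criterion, the pool narrows slightly in a trial that already finds recruitment difficult (SAP 7.1). If more than one frequency stays eligible, each patient's planned frequency must be on record so that the denominator can be derived. The documents do not show whether the CRF captures it.

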### **8.2.4. Follow-Up Visit W13**

All patients will undergo a physical examination, a 12-lead ECG, and be assessed for resolution of pending AEs and SAEs. In addition, safety laboratory assessments will be performed and the pain and lesion scores will be assessed.

### **8.2.5. End of Study Visit**

Patients who withdraw consent or are withdrawn from the clinical trial should, if possible, have an End of Study Visit. This visit should take place as soon as possible after the patient has withdrawn consent or has withdrawn from the clinical trial. The assessments and procedures scheduled for the Follow-Up Visit should be performed at the End of Study Visit.

### 8.3. Restrictions

#### 8.3.1. Contraception Requirements

The use of highly effective contraception methods to prevent pregnancy, of a female participant or a female partner of a male participant, from the day of dosing and for 3 months after the follow-up visit, is necessary.

- Male patients:
  - Male patient who have not had a vasectomy and have a female partner of childbearing potential, must use a condom with spermicide when having heterosexual intercourse, from the time the consent form is signed until 3 months after the last dose of study drug
  - If the male patient's partner is of childbearing potential or if she has had a tubal ligation without having had her ovaries taken out and she is taking a hormonal contraceptive, she may choose to continue taking the hormonal contraceptive but it is strongly recommended to add 1 non-hormonal method of contraception (i.e., male condom with spermicide, female condom, diaphragm with spermicidal jelly or a cervical cap). We strongly recommend the partner, must use reliable forms of contraception during the study and for 3 months after the last dose of study drug
- Highly effective contraceptive methods are:
  - Combined (estrogen and progesterone containing) oral, intravaginal or transdermal contraceptive associated with inhibition of ovulation + condom with spermicide
  - Progesteron-only oral, injectable or implantable hormonal contraception associated with inhibition of ovulation + condom with spermicide
  - Intra uterine device (IUD) + condom with spermicide
  - True abstinence: When this is in line with the patient's preferred and usual lifestyle. Periodic abstinence (e.g., calendar, ovulation, symptothermal (monitoring of your body temperature), post-ovulation methods), and withdrawal are NOT acceptable methods of contraception.
  - Male sterilisation (with the appropriate post-vasectomy documentation of the absence of sperm in the ejaculate).
- Female patients must be in one of the cases described below:
  - Absence of menstruation for 12 consecutive months (menopause) and the doctor confirms they are postmenopausal
  - Both ovaries and uterus have been removed by surgery
  - Cannot get pregnant due to having ovarian problems (confirmed by a doctor)
  - If of childbearing potential, the female patient and their partner have to use highly effective forms of contraception (see above) during the study and for 3 months after the last dose of study drug

## 9. STATISTICAL METHODS

All statistical analyses and programming of tables, figures, and listings will be performed by [REDACTED] using the latest available version of SAS® (SAS Institute Inc., Cary, North Carolina, USA).

Before database lock, a Statistical Analysis Plan (SAP) will be issued as a separate document, providing detailed methods for the analyses outlined below.

Any deviations from the planned analyses as mentioned in detail in the SAP will be described and justified in the final integrated Clinical Study Report.

### 9.1. Clinical Trial Population

#### 9.1.1. Disposition of Patients

Disposition data will be listed and summarised overall. A listing of withdrawals will also be presented including the primary reason for withdrawal.

#### 9.1.2. Protocol Deviations

Deviations from the Clinical Trial Protocol, including deviations of inclusion/exclusion criteria will be assessed as “minor” or “major” in agreement with the Sponsor, prior to database lock.

#### 9.1.3. Analysis Populations

Safety population: All patients who receive at least 1 dose of IMP will be included in the safety population.

Efficacy Population: All patients who receive at least 75% of SNF472 doses and for whom at least baseline and Week 12/EOS images are readable will be part of the Efficacy Population.

### 9.2. General Considerations

All efficacy (ulcer size, Bates-Jensen Wound tool assessments, pain scale, and wound QoL), PK and safety parameters as well as population characteristics will be listed and described using summary statistics. Descriptive statistics (n, mean, standard deviation, median, minimum, and maximum) will be calculated for each quantitative variable (unless otherwise stated). Frequency counts (number of subjects [n] and percentages) will be made for each qualitative variable.

All listings will be sorted by patient number, time-point, and parameter (if applicable).

### **9.3. Demographic and Anthropometric Information, Baseline Characteristics, and Concomitant Medications**

Demographic data will be listed and summarised.

Medical history data will be listed and summarised.

Prior medications are defined as those taken until the time of the first IMP administration. Concomitant medications are defined as those taken at the time of or after the first IMP administration.

Prior and concomitant medication will be coded according to the latest available version of the World Health Organisation's Drug Dictionary (WHO-DD) and the Anatomical Therapeutic Chemical classification system. Prior and concomitant medication will be listed separately.

